### 13.1 Analysis of Local Tolerability

In accordance with the study protocol, local tolerability events of interest (i.e., cough, wheezing, bronchospasm, throat irritation, and change in FEV1) will be documented in the eCRF as AEs. During data analysis local tolerability events of interest thus have to be identified from the CRF form of AEs as follows:

- MedDRA (version 23.1) Preferred Terms (PTs):
  - Cough (MedDRA code 10011224)
  - Wheezing (MedDRA code 10047924)
  - Bronchospasm (MedDRA codes 10006482, 10072338)
  - Throat irritation (MedDRA code 10043521)
  - Change in FEV1 (MedDRA codes 10016987, 10016989, 10016985)
- The version of the utilized dictionary will be presented either in the title or footnote of the provided tables and listings.
- The event must have newly appeared within 1 hour after the end of an IMP inhalation.
- They must have occurred within on or before Visit 3.
- Events meeting the criteria above will be selected independently of the causality assessment of the investigator.

For each local tolerability event, pairwise treatment group comparisons of the proportion of patients with at least one local tolerability event will be performed based on Wilson score 95% confidence intervals (Wilson, 1927).

---

Moreover, incidence densities of events per patient treatment day starting with the first IMP administration will be determined separately for each local tolerability event. In accordance with the visit schedule, incidence densities will be provided for the periods between every two adjacent visits starting with the first IMP administration for the entire randomized treatment period up until Visit 3, and for entire randomized treatment period (as secondary assessment, please refer to section 8.4). Events will be assigned to their period of onset.

In addition to the pairwise treatment group comparisons, all analyses specified above in this section will also be performed for the comparison between all patients treated with L-CsA (2 x 5 mg/day or 2 x 10 mg/day) and those treated with placebo.

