Assessments	
Clinical Trial Plan:
 
At total of 7 visits (Screening, Randomization (Week 0), Week 2, Week 4, Week 8, Week 12 (End of Treatment [EoT]) and Week 14 (End of Study [EoS]) will be performed during the clinical trial. AEs and concomitant medications will be recorded at all visits.
 
Screening: After informed consent has been obtained. Screening Visit procedures will be carried out to check general eligibility for participation up to 4 weeks prior to randomization. Blood will be drawn for safety profiles.
 
Visit 1, Week 0 (Baseline Visit, Randomization): Blood for baseline measures will be collected. Spirometry will be performed. A pregnancy test will be performed for all females of childbearing potential prior to randomization. A physical exam, including vital signs, will be performed. The CGI Questionnaire will be administered. The SF-36 Quality of Life Questionnaire will be administered. Patients will be randomized to study treatment and instructed on use of the L-CsA CCI. The first dose of IMP will be administered under observation and safety will be monitored. Spirometry will be repeated 1 hour \pm 20 min after completion of the first dose of IMP. Blood will be drawn for safety profiles and PK data at pre-dose. PK samples will be obtained directly after end of first inhalation, at 15, 30, and 45 minutes, and 1, 1.5, 2, and 4 hours after end of inhalation. If no tolerability issues are observed, patients will be permitted to leave the clinic. Patients will receive the full IMP supply for the 12 weeks treatment period. The second dose of IMP and all subsequent doses should be inhaled approximately 12 hours after the first dose.
 
Visit 2, Week 2: Spirometry will be obtained. Blood will be drawn for safety profiles and trough levels of CsA. A pregnancy test will be performed for all females of childbearing

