8.3.1 Blinding

This is a single-blind trial. Due to the different appearance of the three tested strengths of IMP, a full blinding of the study was not possible. Only the randomized study patients will be blinded to study treatment assignment. For details of the blinding of the Data Monitoring Committee members, see [Section 12.2](#).

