12.1.5 Tolerability of IMP

Local tolerability findings will be recorded as AEs in the appropriate eCRF.

The patient will be observed for local tolerability findings for 1 hour after inhalation at each on-site study visit.

Local tolerability events are:

- Cough
- Wheezing
- Bronchospasm

- Throat irritation
- Change in FEV₁

In addition, these events will be solicited actively before IMP inhalation at each study visit (except EoS) by questioning the patient whether he/she has experienced any of the events in-between the study visits. If applicable, an AE report form will be completed.

Overall tolerability assessment by the investigator includes:

- CGI questionnaire ([Guy 1976](#))
- Investigator's tolerability assessments at Visit 3 and Visit 5, assessed by means of a five-point verbal rating scale with the response options 'very good', 'good', 'satisfactory', 'moderate', and 'poor'

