13.2.2 Visit 1 / Baseline Visit / Randomization

Baseline Prior to Start of Treatment

- Verify Informed Consent was obtained
- Verify Demographics/Medical History
- Repeat Urine/Serum Pregnancy Test (Urine samples can be collected at the Randomization Visit in order to obtain results quickly while the patient is in the clinic and not delay randomization)
- Physical examination
- Vital signs
- Clinical laboratory tests
- PK blood sample pre-dose
- Spirometry
- Randomization
- Concomitant medications/therapies
- AEs
- CGI (Item 1 only)
- SF-36 questionnaire

Start of Treatment

Following activities will be performed:

- Train patient on L-CsA **CCI** use, drug storage, and inhalation technique
- IMP Administration. Supervise first inhalation for proper use of the nebulizer and for tolerability issues.
- Verify patient is familiar with drug administration and use of nebulizer device
- Emphasize importance of adherence to IMP
- Emphasize importance of adherence to usual medications as taken prior to participating in the trial
- Spirometry: (1 hour \pm 20 minutes after completion of dosing with IMP)
- PK blood samples directly after end of inhalation, 15, 30, and 45 minutes (+/- 5 min), and 1, 1.5, 2, and 4 hours (+/- 15 min.) after end of inhalation
- Local IMP tolerability

Prior to release from clinic, study drug and the nebulizer system for home use will be dispensed to each patient. Patient will receive full IMP supply for the 12 weeks treatment period.

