## 8.3 Primary Endpoints

- Investigational medicinal product (IMP) tolerability and safety during the first 4 weeks of treatment. IMP tolerability will be assessed using the following outcomes:
  - Local Tolerability:
    - Cough
    - Wheezing
    - Bronchospasm
    - Throat irritation
    - Change in FEV1
  - Overall Tolerability:
    - Clinical Global Impressions (CGI) scale
    - Investigator's tolerability assessment
  - Safety:
    - Adverse events (AEs)
    - Serious adverse events (SAEs)
    - Clinical laboratory values
    - Vital signs
    - Physical examination

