### 15.1 Spirometry Measures

For the spirometry measures (FEV1 % predicted, FEV1/FVC, FEV1 absolute, FVC absolute, FVC % predicted), the observed values and corresponding changes from baseline will be summarized using descriptive statistics by parameter and visit. Different methods of measuring will not be distinguished in the descriptive statistics and the statistical model. Baseline spirometry measurement is the last post-bronchodilator assessment at randomization visit (Visit 1) prior to inhalation of IMP which is the following measurement in the eCRF: Before inhalation of IMP (“Before inhalation of 2-4 puffs of salbutamol” if “Before inhalation of IMP” is not available).

For each spirometry measure identified in Section 8.5, treatment group comparisons will be carried out using a mixed model for repeated measures (MMRM), using all available measurements of the outcome of interest. The dependent variables will be the absolute change from baseline of the outcome of interest at the visits scheduled for Weeks 2 through 12, using fixed effects for treatment, visit, and the treatment x visit interaction and the baseline value as a fixed effect covariate. Treatment group comparisons at each visit will be estimated by differences between the marginal (adjusted) means from the treatment x visit interaction, with accompanying p-values and 95% confidence intervals. The analyses will include pairwise treatment group comparisons for each post-baseline visit via contrasts.

For the covariance model of the MMRM analyses, an unstructured covariance matrix should preferably be used. If the model does not converge (e.g., due to the small sample size), a Heterogeneous Toeplitz matrix will be used and, if this model does not converge either, a compound symmetry matrix will be used. If all models fail to converge, patients treated with L-CsA 2 x 5 mg/day or 2 x 10 mg/day will be merged into one group that will be compared to placebo, and the models for the covariance matrix will be applied as before, starting with an unstructured matrix, until the model converges. If none of the models converge, treatment group

comparisons of change versus baseline will be performed for each visit using pairwise, independent samples t-tests on the observed data. Note that the covariance model to be used may be different for different spirometry parameters, depending on whether and when convergence is achieved.

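### The primary item 'Change in FEV1' is counted only from AEs filed by unblinded investigators, and no named analysis uses the FEV1 measured after the first dose

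*SAP*

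**What the plan says.** Protocol 8.1.4 and SAP 8.3 list change in FEV1 with cough, wheezing, bronchospasm and throat irritation as local tolerability. SAP 8.3 places it in the primary assessment over the first 4 weeks: "IMP tolerability will be assessed using the following outcomes".

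**Measurement.** Protocol 13.2.2 lists spirometry before the start of treatment at Visit 1 and again 1 hour ± "20 minutes after completion of dosing with IMP". The synopsis gives the same window ("20 min after completion of the first dose of IMP").

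**Data source for the item.** Protocol 12.1.5 says: "Local tolerability findings will be recorded as AEs in the appropriate eCRF". Protocol 14.2.3.2 compares these items as treatment-emergent AEs. SAP 13.1 follows: "During data analysis local tolerability events of interest thus have to be identified from the CRF form of AEs as follows". For FEV1 it gives three MedDRA codes, and it adds an onset condition: "The event must have newly appeared within 1 hour after the end of an IMP inhalation".

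**Measured spirometry.** SAP 15 and 15.1 treat it as exploratory efficacy in the FAS, with the PPS as sensitivity analysis. The model's response is the "absolute change from baseline of the outcome of interest at the visits scheduled for Weeks 2 through 12".

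**Blinding.** Protocol 8.3.1: "Only the randomized study patients will be blinded to study treatment assignment".

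**The concern.** The trial's primary objective is tolerability and safety, and this is the first study of L-CsA in BOS after allo-HSCT. Protocol 6.1.6 describes good tolerability of the 10 mg dose in native lungs as anticipated. The acute effect of an inhalation on FEV1 is one of the few tolerability items that is actually measured, with a test on each side of the first dose.

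Under the rule as written, that measurement counts towards the primary item only if an investigator who knows the arm decides to file the fall as an AE, under a term that maps to one of three codes, with an onset time inside 1 hour. No size of fall is given to guide that decision. Two sites could treat the same fall differently, and an arm with moderate falls after the first dose could show few or no events. The numbers that would settle the question would be in the database but in no between-arm summary.

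**Working it through.** There is no stated figure to reproduce. The sample size is 3 × 8 = 24, set by feasibility, and the documents give no power, effect size or SD for FEV1.

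**1. Where the Visit 1 post-dose FEV1 could enter an analysis**
- SAP 13 (opening): visit outcomes up to Visit 3 belong to the primary analysis, but no FEV1 method is attached.
- SAP 13.1: AE form only.
- SAP 13.2: CGI and the investigator's tolerability rating.
- SAP 13.3.2: laboratory values, vital signs, physical examination. No spirometry.
- SAP 14.1: repeats Section 13 over the whole treatment period, so it adds no measured FEV1.
- SAP 15.1: the pre-IMP Visit 1 value is baseline and the model responses are Weeks 2 to 12. Descriptive tables are by parameter and visit, with no separate post-dose time point named.
- SAP 9.1: by-visit tabulation of repeated outcomes, and listing of all eCRF data.

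Result: no named analysis uses the value. A listing, or a line in a by-visit table, is the most it can reach.

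**2. The two time windows**
- Spirometry: 60 − 20 = 40 to 60 + 20 = 80 minutes after dosing.
- AE rule in SAP 13.1: up to 60 minutes.
- Share of the spirometry window past the limit: (80 − 60)/(80 − 40) = 50%.

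Protocol 12.1.1 records the time of AE onset. A fall first seen at 61 to 80 minutes may therefore be excluded even if reported, depending on the onset time entered.

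**3. What a zero count says**
With no events, the Wilson 95% upper limit is z²/(n + z²), z² = 3.84.
- One arm: 3.84/(8 + 3.84) = 32.4%.
- Pooled L-CsA: 3.84/(16 + 3.84) = 19.4%.

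For differences against 0/8 I used the hybrid Wilson (Newcombe) interval. At 3/8 it is −2.7% to 69.4%. At 4/8 it is 6.8% to 78.5%, the first count that excludes zero.

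**4. Effect of incomplete reporting (assumed rates, not from the documents)**
P(no event among 8) = (1 − r × s)^8, where r is the true rate of relevant falls and s the share filed as an AE.

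| r | s = 1 | s = 0.5 | s = 0.25 |
|---|---|---|---|
| 20% | 17% | 43% | 66% |
| 30% | 5.8% | 27% | 54% |
| 50% | 0.4% | 10% | 34% |

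**5. What the measured pairs would give**
Half-width of the 95% interval for a difference in mean change = t × SD × √(1/n1 + 1/n2).
- 8 versus 8: 2.145 × √(2/8) × SD = 1.07 × SD.
- 16 versus 8: 2.074 × √(1/16 + 1/8) × SD = 0.90 × SD.

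If the SD of the within-visit change were 0.10 to 0.20 L (assumption), these are 0.11 to 0.21 L and 0.09 to 0.18 L.

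**6. Could 0.150 L from protocol 11.1.1 serve as a cut-off?**
It is a repeatability limit between maneuvers in one session. With a true mean change of zero, normal errors and the same assumed SDs, the share of unaffected patients falling by more than 0.150 L is P(Z > 0.150/0.10 = 1.5) = 6.7% to P(Z > 0.150/0.20 = 0.75) = 22.7%.

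**The case against.** The strongest reply is that the SAP does what the protocol asks. A reader might infer that SAP 13.1 departs from the protocol. It does not: the AE route begins in protocol 12.1.5 and 14.2.3.2, and the SAP adds only the codes and the 1-hour onset condition. This stands, and the gap belongs to both documents. But a rule on how findings are recorded does not prevent a summary of measured values.

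Second, the purpose of the Visit 1 pair is not stated. The repeat test may be a first-dose safety check meant to feed AE reporting, and sites are told to record FEV1 change, to observe for 1 hour and to ask about events. This also stands. It does not supply a reporting threshold, and it leaves the decision with unblinded staff.

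Third, the data are not lost. They will be listed if recorded in the eCRF. Table specifications and eCRF completion guidelines are separate documents not available here, and could hold a post-dose row or a reporting rule. A patient with the Visit 1 pair may also qualify for the FAS, so the SAF/FAS contrast is mainly as-treated versus as-randomized.

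Fourth, a reader might infer that spirometry is the one unbiased measure. Protocol 11.1.1 itself says results depend on cooperation and personal factors, and the examiners are not blinded. It is less discretionary than an AE report, but not free of bias.

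Finally, the added comparison would itself be imprecise at 8 per arm. True, but the whole trial is descriptive and its intervals are wide throughout.

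**Conclusion.** The point holds in a limited form. The primary change-in-FEV1 item depends wholly on AE reports from unblinded investigators, without a stated threshold, and under an onset limit that cuts off half of the permitted spirometry window. Up to 24 measured pre/post pairs enter no named analysis. No alpha, power or sample-size figure is affected, and no estimate is shown to be biased; the reporting shares in the illustration are assumptions.

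The documents do not support saying that the data are discarded, that the SAP contradicts the protocol, or that a 0.150 L fall is a tolerability event. The conclusion rests on the text of the protocol and SAP, and on the separate table specifications and eCRF guidelines not already covering the gap.

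**What to change.** Add to SAP 13.1, in the SAF by treatment received:
- a descriptive summary of the Visit 1 change in FEV1 from pre-dose to post-dose, in litres and percent, with individual values and by-arm statistics;
- pairwise differences, and pooled L-CsA versus placebo, with 95% confidence intervals;
- the bronchodilator status of both measurements. SAP 15.1 takes a post-bronchodilator baseline but allows a pre-salbutamol value as fallback, so pair like with like or flag pairs that differ.

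Keep the AE-based count beside this table. Reconcile the 1-hour onset condition with the 40 to 80 minute spirometry window, so that a fall found at the scheduled test is not excluded from the count. If a categorical cut-off is wanted, the sponsor should pre-specify and justify it; none is proposed here.

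Cost: one SAP paragraph and one table from measurements already scheduled, with no new procedure. The downside is one more set of wide intervals.

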8.3.2.3 Administration of IMP

In clinical trials 12011.201 and clinical trial AI 001 totaling > 1100 patient months of exposure, L-CsA was well tolerated. Patients will be educated regarding use of the L-CsA **CCI** and administration of the first dose will be observed. At subsequent study visits, it will be requested that the patient self-administer a dose of IMP while observed by study personnel.

Each patient will receive two IMP administrations per day, one in the morning and one in the evening. The inhalations are scheduled to be taken approximately 12 hours (but not less than 6 hours) apart, e.g., at 8:00 a.m. and 8:00 p.m. each day. Instructions for administration should be followed as described in the Instructions For Use.

Handling of IMP Inhalation:

Each patient will open a glass vial by lifting up the plastic disk/cap, lifting up the metal flap to remove the metal ring, metal cap, and the rubber stopper. The plastic ampoule containing 1.2 ml or 2.4 mL of the 0.25% NaCl as solvent will be opened by twisting the head part several times in one direction. The NaCl solution will be squeezed into the glass vial containing the whitish lyophilisate cake. The glass vial will be re-closed with the rubber stopper and swirled gently without spilling any liquid for a minimum of 1 minute and up to 5 minutes, until the visible particles are completely dissolved. Shaking of the vial must be avoided to prevent foaming of the reconstituted solution.

Next, the reconstituted IMP should be poured into the L-CsA **CCI** chamber. The nebulizer should be kept horizontal during operation. During inhalation, the patient should sit in an upright position and inhale and exhale deeply through the mouthpiece of the nebulizer without interruption until nebulization shuts off automatically. The solution is for single use only, and no remaining solution should be left in the glass vial. All other clinical trial materials, including unused IMP, must be brought back to the clinical trial center at each scheduled visit for drug and device accountability. After completion of the inhalation, the patient should remove all excess IMP in the mouth and pharynx by rinsing and gargling with water and subsequently discharging the solution.

Interruption of IMP Inhalation:

If a patient needs to temporarily interrupt IMP inhalation (e.g., due to coughing), the patient should turn off the device and turn it back on when ready to resume inhalation.

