10.1.4 Other Medication

All inhaled medications, except investigational inhaled medications, are permissible during the trial.

Patients on bronchodilators should be on a stable dose 4 weeks prior to randomization and throughout the study. All other inhaled medication should be administered after spirometry in the following order: inhaled corticosteroids, inhaled antifungals/antibiotics, and then inhaled IMP. For details with regard to spirometry measurements, please refer to [Section 11.1.1](#).

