The three best values out of the performed maneuvers will be recorded in the eCRF.

Timing of spirometry measures is provided in [Section 10.1.4](#). Timing of spirometry measures in relation to administration of IMP is provided in [Section 13.2](#).

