13.2.3 Visit 2 through Visit 5 / EoT

- Physical examination
- Vital signs
- Clinical laboratory tests
- Cyclosporine A whole blood trough levels (blood sample pre-dose)
- Urine/Serum pregnancy test
- Spirometry
- IMP Administration
- Concomitant medications/therapies
- AEs
- CGI (Items 1-3)
- SF-36 questionnaire
- Local IMP tolerability
- Drug Accountability by vial count (Visit 5 only)
- Check IMP supplies of patient

13.2.4 Visit 3 and Visit 5

- In addition to the assessments described in section 13.2.3, the clinical investigator will perform an Investigator's Tolerability Assessment assessed by means of a five-point verbal rating scale with the response options 'very good', 'good', 'satisfactory', 'moderate', and 'poor'.

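### The SAP's 1-hour rule for Change in FEV1 fits the only scheduled post-dose spirometry (Visit 1, 40 to 80 min) for half of its window, and scheduled tests yield no qualifying event after Visit 1

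*SAP*

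**What the plan says.** SAP 13.1 identifies five local tolerability events from the AE form by MedDRA preferred term; Change in FEV1 is one of them. An event counts only if it meets this condition: "The event must have newly appeared within 1 hour after the end of an IMP inhalation". The section then asks for incidence densities, separately for each event, between adjacent visits, up to Visit 3 and over the whole randomized treatment period. SAP 14.1 repeats the Section 13 analyses over 12 weeks.

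On when FEV1 is measured relative to dosing:

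- Protocol 11.1.1: "Timing of spirometry measures in relation to administration of IMP is provided in" Section 13.2.
- Protocol 13.2.2 (Visit 1): a repeat test at 1 hour ± "20 minutes after completion of dosing with IMP". The synopsis ties it to dose 1: 1 hour ± "20 min after completion of the first dose of IMP".
- Protocol 13.2.3 ("Visit 2 through Visit 5 / EoT"): spirometry appears once, with no post-dose time.
- Protocol 10.1.4: "All other inhaled medication should be administered after spirometry in the following order: inhaled corticosteroids, inhaled antifungals/antibiotics, and then inhaled IMP".
- Protocol 8.3.2.3: "The inhalations are scheduled to be taken approximately 12 hours (but not less than 6 hours) apart".
- Protocol 12.1.5, which includes Change in FEV1 in its event list: "The patient will be observed for local tolerability findings for 1 hour after inhalation at each on-site study visit". It schedules no test for that hour.

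Protocol 14.2.3.2 plans the same densities, and comparisons of events by onset in the first 4 weeks or at any time on treatment. It sets no limit on time since inhalation. The table of differences in SAP Section 6 lists only the renaming of major and minor protocol deviations.

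**The concern.** Cough, wheezing, bronchospasm and throat irritation can be seen or reported after any dose. A change in FEV1 needs a spirometer, and neither document describes home spirometry. A rule that counts only changes arising within an hour of a dose therefore depends on a test being done in that hour, and the schedule provides one such test per patient.

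Two problems follow. At Visit 1 the protocol window and the SAP limit do not match, so a test done on time may not count. After Visit 1 the tables will show interval densities at or near zero in every arm, whatever the drug does, and a printed 0 can be taken for good tolerability when nothing was scheduled to detect the event. The item belongs to the primary assessment of tolerability over the first 4 weeks. SAP 15.1 models Weeks 2 to 12 and names no analysis of the Visit 1 post-dose change, so these AE tables are where an acute effect would have to appear.

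**Working it through.** The documents give no expected event count or density for this item, so there is no plan figure to reproduce. The check is direct arithmetic.

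**Inputs.** SAP limit: 60 min after end of inhalation (SAP 13.1). Visit 1 test: 60 ± 20 min (Protocol 13.2.2). Patients: 8 per arm (Protocol 14.5). Visits at Weeks 0, 2, 4, 8 and 12, so nominal intervals are 14, 14, 28 and 28 days, 84 in total. Visit windows: ±3 days at Weeks 2 and 4, ±7 days at Weeks 8 and 12. Dosing: twice daily.

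**1. Visit 1 window.** Permitted range 40 to 80 min. Share of its width beyond the limit: (80 − 60)/(80 − 40) = 20/40 = 50%. The share of tests beyond it depends on actual timing, which the documents do not give. Assuming normally distributed test times with SD 10 min, it is 31%, 50% or 69% for a mean of 55, 60 or 65 min.

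**2. Scheduled coverage.** Planned doses per patient: 12 × 7 × 2 = 168. Doses followed by a scheduled test: 1, so 1/168 = 0.6%. A pre-dose test at Visits 2 to 5 comes at least 6 hours after the previous inhalation if the dosing gap is kept. It cannot by itself date an onset to within 1 hour of that dose.

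**3. Later intervals.** Qualifying events expected from scheduled tests in V2-V3, V3-V4 and V4-V5: 0 in each arm.

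**4. Dilution.** Let x be the number of Visit 1 events in an arm of 8, with full follow-up and no later events.

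| Period | Patient-days | Density | x = 1, per 100 patient-days |
|---|---|---|---|
| V1-V2 | 8 × 14 = 112 | x/112 | 0.893 |
| To Visit 3 | 8 × 28 = 224 | x/224 | 0.446 |
| 12 weeks | 8 × 84 = 672 | x/672 | 0.149 |

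Relative to V1-V2, the 4-week density is 14/28 = 1/2 and the 12-week density is 14/84 = 1/6. Across the visit windows the 12-week ratio runs from 11/91 = 0.12 to 17/77 = 0.22.

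**5. Illustration of what the schedule can show.** Assume each post-dose test has the same probability p of showing a qualifying change, with p between 0.10 and 0.25 (an assumption). One test per patient gives 8p = 0.8 to 2.0 expected events per arm. If half of these were lost to the 60-min limit, 0.4 to 1.0 would remain. A post-dose test at all five visits would give 40p = 4.0 to 10.0.

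**6. A related conflict.** SAP 13.1 also restricts qualifying events to those on or before Visit 3. Read literally, that empties the later intervals for all five items and contradicts the whole-period densities requested in the same section and in SAP 14.1.

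**The case against.** The strongest reply is that these events are AEs reported by the investigator, not flags generated by a test. Protocol 12.1.5 requires an hour of observation after inhalation at each on-site visit and active questioning before inhalation. Protocol 13.2.6 allows unscheduled visits with the 13.2.3 assessments, spirometry among them. Protocol 12.1.1 records the time of AE onset. A qualifying event after Visit 1 is therefore possible. This stands, and it rules out three stronger readings that a reader might infer:

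- *That later events are impossible.* The documents support this only for scheduled tests.
- *That the 12-week density falls to about zero.* It includes the Visit 1 events, so it is diluted. Only the later-interval densities tend to zero.
- *That half of the Visit 1 falls are discarded.* The 50% is a share of the window's width, not of tests. A fall found at 70 min is lost only if its onset is entered as the test time, and neither document says how onset of an FEV1 change is timed.

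The order of items in Protocol 13.2.3 is also weak evidence, because such lists are not strictly chronological: 13.2.2 puts the 1-hour spirometry ahead of the blood sample taken directly after inhalation. The pre-dose timing rests on 10.1.4 and on the absence of any post-dose time in 13.2.3.

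It can also be said that the information survives elsewhere. FEV1-decrease AEs that fail the 1-hour rule still enter the TEAE tables by SOC and preferred term (SAP 13.3.1), and SAP 15.1 summarises FEV1 by visit. This limits the damage. It does not repair the local tolerability table, and the by-visit summaries are efficacy outputs on the FAS.

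Finally, if only dose 1 is followed by a scheduled test, most of V1-V2 is unobserved as well. That is correct. The factors of 2 and 6 are ratios of patient-time, and the V1-V2 density is not a sound rate either, which argues for a proportion among patients tested.

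**Conclusion.** The point holds for scheduled testing. The SAP adds a 1-hour filter that the protocol's analysis section does not contain and that the SAP does not declare. It fits half the width of the window for the one test able to satisfy it, and that test follows 1 of 168 planned doses. Densities for V2-V3, V3-V4 and V4-V5 carry no information on this item from scheduled spirometry. The 4-week and 12-week densities are about one half and one sixth of the V1-V2 value.

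These sizes assume nominal visit timing, complete follow-up, 8 patients per arm and no unscheduled post-dose tests. The loss of falls found at 61 to 80 min further assumes that onset is recorded as the test time.

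The effect is on what the tables can mean. It applies to all arms alike and no between-arm bias has been shown. The trial is descriptive, and this is one of five local tolerability items. It is still part of the primary assessment, and the correction is cheap enough to make before the data are analysed.

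**What to change.** Changes to SAP wording and table shells only:

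1. For Change in FEV1, accept any Visit 1 post-dose test within the protocol window, up to 80 min after end of inhalation, and state how onset of an FEV1 change is timed.
2. Make the main summary of this item the proportion of patients with an acute change among those tested after dose 1.
3. Keep later events from unscheduled tests or investigator-assigned onset in the tables and listings. Mark the later-interval and whole-period densities *no scheduled post-dose spirometry*. Do not blank them: that would hide genuine events and drop a density that Protocol 14.2.3.2 requires.
4. Also tabulate FEV1-decrease AEs without the 1-hour filter, as Protocol 14.2.3.2 specifies.
5. List the filter as a change in SAP Section 6.
6. Reconcile Protocol 12.1.5, Protocol 13.2.3 and SAP 13.1 on whether FEV1 is to be assessed in the hour after inhalation at later visits, and limit the on-or-before-Visit-3 condition in SAP 13.1 to the 4-week analysis.

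The cost is one extra table and a less simple density display for one of five items.
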